# 10.5.7 Pharmacokinetics Data

# 10.5.8 Technical Data

Technical success is defined as:

- Successful adhesion of the patch to the target lesion.
- Successful delivery (including release and permeation) of the drug to the target lesion, without getting to surrounding oral surfaces.
- Successful peel of the used patch after 10 minutes without damaging the target lesion underneath.

# 11 QUALITY CONTROL AND QUALITY ASSURANCE

Quality Assurance (QA) and Quality Control systems will be implemented and maintained with Standard Operating Procedures by Privo Technologies, as appropriate, to ensure that this clinical study is conducted and data are generated, documented and reported in compliance with the Protocol, ICH E6 GCP and applicable regulatory requirements.

Before enrolling any subjects in this study, a Sponsor representative and the Investigator will review the Protocol, IB, CRFs and instructions for their completion, as well as the procedures for obtaining informed consent and for reporting TEAEs and SAEs. A qualified representative of the Sponsor will monitor the conduct of the study by visiting the site and by contacting the site by telephone and email. During site visits, the study Monitor will assure accurate and reliable data collection by verifying the information recorded on the CRFs against source documents and medical records (ie, source document verification).

Measures will be undertaken to protect the confidentiality of records that could identify subjects respecting the privacy and confidentiality rules in accordance with applicable regulatory requirements.

# **12 DOCUMENTATION AND INSPECTIONS**

### 12.1 Study Monitoring

The Sponsor has responsibility to governing regulatory authorities to take all reasonable steps to ensure the proper conduct of the study with respect to trial ethics, Protocol adherence, and data integrity and validity.

This trial will be closely monitored by Sponsor representatives throughout its duration. Monitoring will be in the form of personal visits with the Investigator and staff as well as any appropriate communications by telephone, mail, or email transmission.

The personal visits and monitoring are conducted to the extent possible however under certain circumstances such as COVID-19 pandemic, to minimize or eliminate immediate hazards or to protect the life and well-being of research staff and participants, discussions, monitoring and site closures will be performed remotely via technologies including but not limited to phone calls, email, eCRF, eTMF and file sharing on video conferencing for source documents. Sponsor and sites can utilize video and teleconferencing such as ZOOM to remotely discuss, review and approve documents. The PI sign off can be obtained and saved electronically for all eCRFs at the site.

The purpose of these contacts is to review trial progress, Investigator and subject adherence to the protocol, and to determine if there are any problems associated with the conduct of the study. The following may be assessed during site monitoring visits:

- Required regulatory documentation
- Signed ICFs
- Subject accrual and follow-up
- Study drug inventory records
- Investigator and subject compliance to the study Protocol
- Concomitant therapy uses
- AE documentation
- Protocol deviation documentation
- Data are accurate, complete, and verifiable when compared to source documents

The Investigator and study staff are expected to cooperate with monitors during such visits and provide all relevant study documents.

# 12.2 Audits and Inspections

All documentation pertaining to this clinical trial may be subject to a QA audit by the Sponsor, or the FDA. Upon request, the auditor will have access to inspect, copy, review, and audit all source documents, CRFs, medical records, correspondence, and ICFs pertaining to the subjects in the trial. The Investigator agrees to promptly take any reasonable steps that are requested by

the Sponsor as a result of an audit to cure deficiencies in the study documents and CRFs. Other documentation subject to QA audit includes the IRB files, certification and quality control of supporting laboratories, and records relevant to the trial in any supporting pharmacy facilities. Conditions of storage of study materials are also subject to inspection. Sponsor representatives may observe the conduct of any aspect of the clinical trial or its supporting activities both within and outside of the Investigator's institution.

# **13** ETHICAL AND LEGAL ISSUES

# 13.1 Ethical Conduct/Good Clinical Practice

This study will be conducted in accordance with the ethical principles that have their origin in the current Declaration of Helsinki and will be consistent with ICH GCP and applicable regulatory requirements.

## 13.2 Institutional Review Board

This study must be reviewed and approved by the IRB representing the institution prior to enrolling subjects. The IRB must be appropriately constituted and meet all requirements as described in Part 56, Title 21 of the US CFR. The review must include both the Protocol and the ICF for the trial. A copy of the Letter or Notice of Approval from the IRB must be received by the Sponsor prior to shipment of drug supplies to the Investigator. The IRB membership list must be submitted to the Sponsor with the written IRB approval and updated lists, if applicable.

The Investigator must promptly report all changes in the research activity and all unanticipated problems involving risk to the subjects or others to their IRB. The Investigator will provide progress reports as required by the IRB. The Investigator is responsible for assuring continuing review and approval of the clinical study on an annual basis and submitting documentation of renewal to the Sponsor. The Investigator will give notice to the IRB when participation in the study has been completed.

# 13.3 Written Informed Consent

The Investigator agrees to protect the rights, safety, and welfare of the subjects entered into the study, including obtaining written informed consent prior to performing any study-related procedures and informing each subject that the study drug is being used for investigational purposes. A copy of the IRB-approved ICF to be used during the study must be submitted for Sponsor review prior to study initiation.

Prior to entry into the study, the purpose and nature of the study and possible AEs must be explained to each patient. All questions about the study should be answered to the patient's satisfaction or the patient's legal representative. It is the responsibility of the Investigator or designee to obtain written informed consent from each patient, thereby attesting that consent was freely given. A copy of the signed and dated ICF will be given to the patient. Documentation of the informed consent process must be evident in the patient's clinical files, and the original executed ICF must be available for review by the study Monitor.

# 13.3.1 Update of Informed Consent

In the event that modifications in the experimental design, dosages, parameters, subject selection, etc., of the Protocol are indicated or required, and in the event that such modifications substantially alter the study design or increase the potential risk to subjects, revisions to the existing ICF will be made. Such a revision will be reviewed and approved by the appropriate IRB, and documentation of this approval will be forwarded to the Sponsor for submission to the appropriate regulatory body.

In addition, all current study participants, as well as subsequent study candidates, will be informed of the study design modification or increase in potential risk, and written informed consent will be obtained as outlined in Section 13.3.

## 13.4 Records and Case Report Forms

The Investigator is required to prepare and maintain adequate and accurate case histories designed to record all observations and other data pertinent to the investigation on each individual treated with the study drug. Data reported on the CRF that are derived from source documents must be consistent with the source documents or the discrepancies must be explained. All requested information must be entered on the CRF in the spaces provided.

The confidentiality of records that could identify subjects must be protected, respecting the privacy and confidentiality rules in accordance with the applicable regulatory requirements.

The completed CRF must be promptly reviewed, signed, and dated by a qualified physician who is an Investigator or Sub-Investigator. The Investigator must retain a copy of the CRFs including records of the changes and corrections.

# **13.5 Protocol Deviations**

The study is to be conducted as described in this Protocol without deviation unless there is a safety concern. The Protocol should not be modified for any subject without the prior consent of the Sponsor and, if necessary, the IRB responsible at the investigative site.

In the event of an important deviation, a report will be submitted to the IRB (as applicable) and site explaining the circumstances.

# 13.6 Retention of Records

US federal law requires that the Investigator retain copies of all files pertaining to the trial (ie, medical records, laboratory reports, drug inventory/disposition records, signed ICFs, CRFs, all correspondence, dates and reports of monitoring visits) for a period of 2 years following the date of marketing application approval of the drug for the indication investigated in the study, and until there is no pending or contemplated marketing application, or for 2 years following the Sponsor's discontinuing worldwide clinical development of the study drug, as notified by the Sponsor, whichever is longer.

If the Investigator relocates, retires, or withdraws for any reason from the study, trial records may be transferred to an acceptable designee, such as another Investigator within the institution.

Prior notice of such transfer will be provided in writing to the Sponsor. The Investigator must obtain written permission from the Sponsor prior to disposing of any records.

1.1 Background

Squamous cell carcinomas (SCC) of the head and neck include tumors that occur in the oral cavity. Most lip and oral cavity cancers originate in squamous cells, the thin flat cells that line the lips and oral cavity. Risk factors for oral cancer include chronic heavy use of alcohol and tobacco, long periods of exposure to natural or artificial sunlight, and exposure to human papillomavirus. The 5-year survival rate for oral cancer is approximately 60%; diagnosis at an early stage significantly increases the 5-year survival rate. Oral cancer has a high rate of recurrence (18%–76% for subjects who undergo standard treatment). Approximately 1/3 of subjects treated with surgery and adjuvant therapy will experience local or regional recurrence and/or distant metastasis.

The most common chemotherapy drugs for advanced oral cancer includes cisplatin, methotrexate, carboplatin, 5-fluorouracil, paclitaxel, and docetaxel, which when administered alone or in combination have been shown to provide clinical benefit with demonstrated improvement in overall survival.

PRV111 (Cisplatin Transmucosal System) is a thin, 2-layer, self-adhesive transmucosal patch embedded with cisplatin and a non-woven fabric adhesive backing. In addition to the PRV111 drug product, a separately packaged Permeation Enhancer Powder for Reconstitution is used in conjunction with the PRV111 drug product. The reconstituted Permeation Enhancer Solution is applied prior to the administration of PRV111 to improve the absorption of the cisplatin active ingredient.

Privo's PRV111 is intended as a local induction chemotherapy, to improve the local control of the disease prior to surgery by shrinking the tumor size. Local cisplatin delivery may result in larger and more effective doses of cisplatin delivered to the tumor while significantly reducing or eliminating the systemic toxicities and side effects traditionally associated with intravenous (IV) cisplatin chemotherapy. Treatment with cisplatin which is targeted to the tumor site and not administered systemically may reduce the dose-limiting systemic toxicities that are observed with IV cisplatin administration. If proven safe and effective for the treatment of SCC of the oral cavity, PRV111, in association with the standard care, may decrease the risk of local tumor recurrence.

2 Trial Design

2.1 Study Objectives

Primary Objectives

- Determine a safe and efficacious dose of PRV111 (Cisplatin Transmucosal System) (cisplatin drug-loaded patch + permeation enhancer [PE]) under the conditions of the trial.

Secondary Objectives

- Evaluate tumor volume shrinkage
- Assess long-term safety of the treatment
- Evaluate device technical success including the residual cisplatin level in the patch after the application period
- Evaluate systemic, tumor and lymph node (if available) platinum levels following administration

2.2 Study Design

This is a two-stage adaptive design. The First stage with 6 patients focuses on determining a safe dose, while stage 2 expands the study at the previously determined dose. See the Protocol section on synopsis.

Methodology: This is a Phase 1/2, open-label, prospective, single-arm study of the safety and efficacy dose-finding, systemic exposure, and device technical success of PRV111 (Cisplatin Transmucosal System) (cisplatin drug-loaded patch+PE) in subjects with oral squamous cell carcinoma (SCC) amenable to surgery.

Study Design: This is a 2-stage adaptive study. For Stage 1, up to 10 subjects will be enrolled for the purpose of 5 evaluable subjects for the 1st stage of the study to determine a safe and efficacious dose. For Stage 2, the target goal is up to 11 evaluable subjects for the efficacy analysis of the final dose. If the dose remains the same as Stage 1, Stage 2 will target 6 additional evaluable subjects but up to 21 subjects will be recruited if the dose is changed between Stage 1 and 2.

For the purpose of dose selection, tolerable dose is defined as a dose where fewer than 33% of subjects being evaluated within the safety population present with dose-limiting toxicities (DLTs). Effective dose is determined based on the evaluable population as described in the Statistical Methods section.

The 2 stages of the study are described below:

Stage 1: Up to 10 subjects will be enrolled for the purpose of 5 evaluable subjects and undergo 3 treatment applications at each of the 4 planned treatment visits. Each treatment visit will include 1 application of the PE. Starting approximately 5 minutes after application

of the PE, 1 or 2 patches (depending on tumor size) will be applied. A total of 3 treatment applications of patches will occur. These successive applications will span approximately 35 minutes. The 3 applications provide a total of 6 mg of cisplatin per visit (12 mg if 2 patches are applied at the same time). The 4 treatment visits will be separated by 2 to 4 days (at least 48 hours).

The following decisions will be made based on safety and efficacy of the dose:

Dosing Rules for Stage 1:

- 1) If fewer than 2 subjects experience DLTs, then the following scheme will be considered for stage 2 dosing:
 - a. If fewer than or equal to 2 of the evaluable subjects have a response (Defined in the efficacy table) the dose will be escalated from 3 to 5 treatment applications per treatment visit for Stage 2.
 - b. If 3 or more evaluable subjects have a response (CR or PR), the dose will remain the same for Stage 2 (3 applications per treatment visit).
- 2) If 2 or more subjects experience DLTs at any time during Stage 1, the following scheme will be considered for dose de-escalation in Stage 2:
 - a. If there are 6 evaluable subjects in Stage 1:
 - If out of 6 evaluable subjects, 2 or more subjects have a response (CR or PR), the dose will be de-escalated to 2 applications per treatment visit.
 - If out of 6 evaluable subjects, fewer than 2 have a response (CR or PR), the dose will be considered intolerable and the study will be stopped.
 - b. If Stage 1 dosing was stopped prior to having 6 evaluable subjects, the dose will be de-escalated from 3 applications to 2 applications per treatment visit.

Stage 2: In case of dose escalation or de-escalation, Stage 2 will be conducted in 2 parts: Stage 2a and Stage 2b.

Subjects will receive 2, 3, or 5 treatment applications at each of the 4 planned treatment visits, depending on the results of Stage 1. Up to 21 additional subjects will be enrolled in Stage 2 if necessary, for the purpose of 16 total evaluable subjects at the final dose for the efficacy analysis.

Stage 2a: This stage will include 6 subjects (Stage 2a flowcharts). In this stage, only safety outcomes will be considered for determining the dosing regimen for the set of subjects to be enrolled in Stage 2b. All subjects enrolled in this stage will be monitored for possible DLTs.

- 1) If fewer than 2 subjects with DLTs in Stage 2a, enrollment will continue for the remaining number of subjects required in Stage 2b at the same dose.
- 2) If 2 subjects experience DLTs in Stage 2a, dosing will be re-considered. It may be stopped or, when possible, decreased for the remaining subjects enrolled in Stage 2b:
 - a. If “Stage 2a - Escalated Dose”, the original dose will be used for up to 10 additional evaluable subjects enrolled for Stage 2b.
 - b. If “Stage 2a - Same Dose”, dosing will be stopped. Additional subjects, for up to 10 evaluable subjects, will be enrolled for Stage 2b at a lower dose, consisting of 2 applications per treatment visit.

- c. If “Stage 2a – De-escalated Dose”, the study will stop, as no safe dose could be determined.

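### SAP 2.2 keeps counts of 6, 10 and 16 where the SAP's own design and Protocol 6.1 use 5 and 11, so two DLT-driven dosing decisions differ between the documents

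*SAP*

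**What the plan says.** SAP 2.2 gives two sizes for Stage 1. Its lead sentence has 6: "The First stage with 6 patients focuses on determining a safe dose". The study design paragraph that follows has 5: "For Stage 1, up to 10 subjects will be enrolled for the purpose of 5 evaluable subjects".

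The rules for two or more DLTs use 6. Rule 2a splits on response only when 6 subjects are evaluable, and it stops the study on this condition: "If out of 6 evaluable subjects, fewer than 2 have a response (CR or PR"). Rule 2b covers the rest: "If Stage 1 dosing was stopped prior to having 6 evaluable subjects, the dose will be de-escalated".

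For Stage 2, SAP 2.2 says "In case of dose escalation or de-escalation, Stage 2 will be conducted in 2 parts". It then gives Stage 2a 6 subjects, sets enrolment "for the purpose of 16 total evaluable subjects at the final dose", and allows up to 10 further evaluable subjects in Stage 2b in two branches. One of these is a branch for an unchanged dose.

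Other parts of the plan use 5 and 11:

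- SAP 5.1 has n1 = 5, r1 = 2, N = 11, R = 6, and caps DLTs at fewer than 2 in 5 new subjects.
- SAP 3.1.2 sets success at 7 of up to 11 evaluable subjects.
- Protocol 6.1 uses 5 in Stage 1 rules 2a and 2b, 5 for Stage 2a and 11 at the final dose. It ends dosing in Stage 2b at 3 subjects with DLTs.
- SAP 7 declares no departures from the Protocol.

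The response wording also varies. SAP rule 1b reads "If 3 or more evaluable subjects have a response (CR or PR"), and rule 2a does the same, leaving out strong response (SR). SAP 3.1.1 and Protocol 6.1 count CR, SR or PR. The short form also appears in the hypothesis statements of SAP 5.1 and Protocol 10.2.

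**The concern.** These counts are thresholds in rules that decide whether the study stops, de-escalates or continues, and those rules serve the primary objective of finding a safe and efficacious dose. If the threshold is 6 and the stage is planned to end at 5, the response-based stop in SAP rule 2a cannot be reached at the SAP's own target. A Stage 2a that is one subject larger also changes which DLTs count towards its rule. Someone applying SAP 2.2 could therefore take a different dosing decision from someone applying Protocol 6.1, with no declared change to explain it.

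**Working it through.** **1. Which size is intended.** Inputs from SAP 5.1 and Protocol 10.2: n1 = 5, r1 = 2, N = 11, R = 6, p0 = 0.30, p1 = 0.85. (One sentence in SAP 5.1 has 0.65; its table and the Protocol have 0.85.)

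P(reject | p) = Σ over x = 3..n1 of Bin(x; n1, p) × P(Y ≥ 7 − x | 11 − n1, p)

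With n1 = 5 and p = 0.30: 0.1323 × 0.0705 + 0.0284 × 0.2557 + 0.0024 × 0.5798 = 0.0180. At p = 0.85 the sum is 0.9644. Both match the stated 0.018 and 96.44%. With n1 = 6 and the rest unchanged, the results are 0.0208 and 0.9817. The stated figures fit 5, not 6.

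**2. Stage 1 rules side by side** (0 to 5 evaluable subjects, SR counted as response).

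| DLT subjects | Evaluable | Responses | Protocol 6.1 | SAP 2.2 |
|---|---|---|---|---|
| 0 or 1 | 5 | 0 to 2 | escalate | escalate |
| 0 or 1 | 5 | 3 to 5 | same dose | same dose |
| 2 or more | below 5 | any | de-escalate | de-escalate |
| 2 or more | 5 | 2 to 5 | de-escalate | de-escalate (2b), or no rule |
| 2 or more | 5 | 0 or 1 | **stop** | **de-escalate (2b), or no rule** |

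The no-rule reading arises if Stage 1 counts as complete at 5, because rule 2b is worded for dosing stopped early. The last row is decision (a).

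**3. Stage 2a rules side by side** (first six subjects after a dose change).

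| DLTs in subjects 1 to 5 | DLT in subject 6 | Protocol 6.1 | SAP 2.2 |
|---|---|---|---|
| 2 | either | Stage 2a rule 2 | Stage 2a rule 2 |
| 1 | yes | **subject 6 is in Stage 2b; dosing stops only at 3** | **Stage 2a rule 2: back to the original dose, or stop if already de-escalated** |
| 1 | no | continue | continue |
| 0 | either | continue | continue |

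The second row is decision (b).

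**4. Size of (a).** P(0 or 1 of 5 respond) = (1 − p)^5 + 5p(1 − p)^4 = 0.528 at p = 0.30, 0.188 at 0.50 and 0.002 at 0.85. The documents give no DLT rate q, so 0.10, 0.20 and 1/3 are assumed. P(2 or more DLTs in 5) = 1 − (1 − q)^5 − 5q(1 − q)^4 = 0.0815, 0.2627 and 0.5391. Assume also that 5 are enrolled, all are evaluable, and DLTs are independent of response. The products are then:

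- p = 0.30: 0.043, 0.139, 0.285
- p = 0.85: 0.0002, 0.0006, 0.0012

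The probability is 0 if subjects are dosed one at a time, dosing stops at the second DLT, and subjects with a DLT are not evaluable.

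**5. Size of (b), given that Stage 2a is opened.** P(one DLT in five, then a DLT in the sixth) = 5q(1 − q)^4 × q = 5q²(1 − q)^4:

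- q = 0.10: 5 × 0.01 × 0.6561 = 0.033
- q = 0.20: 5 × 0.04 × 0.4096 = 0.082
- q = 1/3: 5 × 0.1111 × 0.1975 = 0.110

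**6. Other leftover counts.** The 16 equals 6 + 10, which suggests one older scheme behind all these counts. The same-dose branch under Stage 2a cannot be reached, because Stage 2a opens only after a dose change.

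**The case against.** The strongest objection is that this is leftover text in a design recap. Dosing decisions are conduct, and Protocol 13.5 requires the study to be run as the Protocol describes. SAP 2.2 itself adds "See the Protocol section on synopsis". The analysis sections of the SAP are right. In case (a) the SAP would move subjects to 2 applications per visit instead of 3, so nobody receives more drug per visit, and two DLTs in a de-escalated Stage 2a would still stop the study. This stands and limits the practical risk. It does not make the wording right: the SAP contradicts itself on 5 and 6, and its stop branch is out of reach at its own target.

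A second objection concerns versions. The SAP is based on Protocol Amendment 5, and the available Protocol text does not show its version, so the statement in SAP 7 cannot be held firmly against this Protocol. That is fair, but the conflict inside the SAP does not depend on it.

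Third, the probabilities rest on assumed DLT rates, and in (a) on full evaluability. Up to 10 subjects may be enrolled, a subject with a DLT stops dosing (Protocol 8.4), and evaluability needs 3 of 4 visits (SAP 5.2.2). This also stands: the figures show a range and do not predict.

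Fourth, a reader might infer from the response wording that a subject with SR would not count as a responder. The documents do not support that. SAP 3.1.1 includes SR, rule 1a refers to the efficacy table, and SAP 3.1.2 speaks of PR as a minimum. The short form needs aligning, but it is secondary.

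**Conclusion.** The counts in SAP 2.2 are wrong as written and should be corrected. They change two decisions, in opposite directions: in (a) the SAP continues at a lower dose, or gives no rule, where the Protocol stops; in (b) the SAP reduces the dose or stops where the Protocol continues. Case (a) is most likely when the drug is toxic and inactive, and close to negligible at the design response rate of 0.85. Case (b) does not depend on response once Stage 2a is open.

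Two stronger readings are tempting. One is that the sample size, type I error or power is affected. It is not: those figures use n1 = 5 and N = 11 and reproduce exactly. The other is that nothing in the documents settles the conflict. Protocol 13.5 settles it for conduct, so the remaining risk is someone working from SAP 2.2 alone. That 5 is intended follows from the recomputation and does not rest on any assumed DLT rate.

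**What to change.** In SAP 2.2:

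1. Change 6 to 5 in the lead sentence, in Stage 1 rules 2a and 2b, and in the Stage 2a size.
2. Change the final-dose total from 16 to 11.
3. In the escalated-dose branch of Stage 2a, replace the allowance of up to 10 further evaluable subjects with the Protocol's rule, which returns the remaining subjects to the original dose.
4. Replace the unreachable same-dose branch with the Protocol's Stage 2b rule (no further dosing at 3 subjects with DLTs). Deleting it alone would leave the available SAP text with no DLT rule for an unchanged dose in Stage 2.

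As a secondary alignment, list CR, SR or PR as response in SAP rules 1b and 2a, SAP 5.1 and Protocol 10.2. A separate precedence statement is not needed, given Protocol 13.5.

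The cost is wording: corrections to the SAP and one clarification in Protocol 10.2. No subjects or procedures are added, and type I error and power do not change. With these edits, rows (a) and (b) above agree with the Protocol.

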# **Dosing Rules for Stage 1:**

- 1) If fewer than 2 subjects experience DLTs, then the following scheme will be considered for Stage 2 dosing:
  - a. If fewer than or equal to 2 of the evaluable subjects have a response (as tumor volume PCFB complete response [CR], strong response [SR] or partial response [PR])) the dose will be escalated from 3 to 5 treatment applications per treatment visit for Stage 2.
  - b. If 3 or more evaluable subjects have a response (as tumor volume PCFB complete response [CR], strong response [SR] or partial response [PR])), the dose will remain the same for Stage 2 (3 applications per treatment visit).
- 2) If 2 or more subjects experience DLTs at any time during Stage 1, the following scheme will be considered for dose de-escalation in Stage 2:
  - a. If there are 5 evaluable subjects in Stage 1:
    - If out of 5 evaluable subjects, 2 or more subjects have a response (as tumor volume PCFB complete response [CR], strong response [SR] or partial response [PR])), the dose will be de-escalated to 2 applications per treatment visit.
    - If out of 5 evaluable subjects, fewer than 2 have a response (as tumor volume PCFB complete response [CR], strong response [SR] or partial response [PR])), the dose will be considered intolerable and the study will be stopped.
  - b. If Stage 1 dosing was stopped prior to having 5 evaluable subjects, the dose will be de-escalated from 3 applications to 2 applications per treatment visit.

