#### c.

#### Figure 2. Stage 1 dose determination scheme

d) Target Dose for Stage 2a

*Stage 2:* In case of dose escalation or de-escalation, Stage 2 will be conducted in 2 parts: Stage 2a and Stage 2b.

Subjects will receive 2, 3, or 5 treatment applications at each of the 4 planned treatment visits, depending on the results of Stage 1. Up to 21 additional subjects will be enrolled in Stage 2 if necessary, for the purpose of 11 total evaluable subjects at the final dose for the efficacy analysis.

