#### Stage 2a:

This stage will include 5 subjects (Stage 2a flowcharts). In this stage, only safety outcomes will be considered for determining the dosing regimen for the set of subjects to be enrolled in Stage 2b. All subjects enrolled in this stage will be monitored for possible DLTs.

- 1) If fewer than 2 subjects with DLTs in Stage 2a, enrollment will continue for the remaining number of subjects required in Stage 2b at the same dose.
- 2) If 2 subjects experience DLTs in Stage 2a, dosing will be re-considered. It may be stopped or, when possible, decreased for the remaining subjects enrolled in Stage 2b:
  - a. If "Stage 2a Escalated Dose", the original dose will be used on the remaining patients.

b. If "Stage 2a - De-escalated Dose", the study will stop, as no safe dose could be determined.

a) Stage 2a Enrollment Goal: 5 subjects
b) 2 subjects with DLTs, evaluated based on Safety Subjects
c) Target dose for Stage 2b

Figure 3. Stage 2a safety scheme in case of escalated dose decision

Figure 4. Stage 2a safety scheme in case of de-escalated dose decision

**Stage 2b:** In this stage both safety and efficacy will be evaluated. All subjects will be monitored for possible DLTs (Stage 2b – All Doses flowchart).

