#### **Stopping Rules at Stage 2b:**

If 3 subjects with DLTs, no additional subjects will be dosed.

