#### **10.2** Sample Size Determination

Safety outcomes resulting in DLT will be used during the conduct of this study to select doses being tested according to pre-defined thresholds of toxicity.

- Local and systemic safety and tolerability will be summarized using descriptive statistics.
- The number of subjects with DLTs will be capped to be fewer than 2 subjects with DLTs out of 5 new subjects enrolled.
- The treatment regimen will be deemed tolerable if fewer than a third of the subjects exposed to it present DLTs.
- Efficacy based on Tumor volume CFB criteria will be summarized, and the null hypothesis that the probability of response is at most 30%, where a response is the occurrence of CR or PR will be tested using a one-sided test exact binomial test at level 0.018.
- •
- Variables measuring technical success (including residual cisplatin level in the patch) will be summarized using descriptive statistics.

At the end of Stage 2, the following is a statistical analysis of the sample size as it pertains to efficacy:

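### SAP 2.2 runs the Stage 2a two-DLT gate on 6 subjects where Protocol 6.1 runs it on 5, in an SAP block that is not aligned with the 11-subject design

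*SAP*

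**What the plan says.** Stage 2a exists only if the dose changes after Stage 1. In Protocol 6.1: "In case of dose escalation or de-escalation, Stage 2 will be conducted in 2 parts: Stage 2a and Stage 2b". SAP 2.2 states the same condition.

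The Protocol fixes the size of Stage 2a twice, in the text ("This stage will include 5 subjects (Stage 2a flowcharts") and in the figure legend ("Stage 2a Enrollment Goal: 5 subjects"). SAP 2.2 has "Stage 2a: This stage will include 6 subjects (Stage 2a flowcharts".

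The consequences attached to the gate are the same in both documents. Fewer than two DLTs lets the changed dose continue. Two DLTs return an escalated dose to the original dose, or end the study at a de-escalated dose.

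Three further statements bear on the gate:

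- Protocol 10.2 and SAP 5.1 cap DLTs at fewer than 2 out of 5 new subjects. The sentence does not name Stage 2a, but its denominator is 5.
- Protocol 6.1 has a later stop in Stage 2b: "If 3 subjects with DLTs, no additional subjects will be dosed". SAP 2.2 states no Stage 2b stop.
- Protocol 10.2 defines tolerability: "The treatment regimen will be deemed tolerable if fewer than a third of the subjects exposed to it present DLTs".

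SAP 7 says that no changes from the Protocol are planned.

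**The concern.** The gate decides whether a changed dose survives, and finding a safe and efficacious dose is the primary objective. With the same trigger on two different denominators, teams working from the two documents can reach different decisions on the same data.

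The 6 is also not a lone misprint. The same SAP block opens with a first stage of 6 patients, uses 6 evaluable subjects throughout rule 2 of the Stage 1 dosing rules, allows up to 10 evaluable subjects in Stage 2b and totals 16 evaluable subjects at the final dose. It also contains a Stage 2a branch for an unchanged dose. The Protocol has none of these. Its Stage 1 rule reads "If there are 5 evaluable subjects in Stage 1", and its Stage 2 enrolls "for the purpose of 11 total evaluable subjects at the final dose for the efficacy analysis". The SAP disagrees with itself as well: the second study-design paragraph of SAP 2.2 gives 5 evaluable subjects in Stage 1 and up to 11 at the final dose, SAP 3.1.2 defines success as 7 of up to 11, and SAP 5.1 tabulates n1 = 5 and N = 11.

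**Working it through.** **1. Which design the stated error rates belong to.** Inputs from Protocol 10.2: n1 = 5, r1 = 2, N = 11, R = 6, null rate 0.30, alternative 0.85. Formula: sum over x = 3, 4, 5 of P(x of 5) × P(at least 7 − x of 6).

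- At 0.30: 0.13230 × 0.07047 + 0.02835 × 0.25569 + 0.00243 × 0.57983 = 0.01798. Stated: 0.018.
- At 0.85: 0.13818 × 0.95266 + 0.39150 × 0.99411 + 0.44371 × 0.99960 = 0.96437. Stated: 96.44%.

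Both figures reproduce with 5 and 11. The 6 and 16 in SAP 2.2 do not belong to this design. The size of Stage 2a does not enter the calculation.

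**2. How the 16 is made up.** In the escalated-dose branch of SAP 2.2, the up-to-10 subjects receive the original dose after the Stage 2a dose has been abandoned. They therefore add to Stage 1: 6 + 10 = 16.

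**3. Gate probability, given that Stage 2a is reached.** The documents give no true DLT rate d, so 10%, 20% and one third are assumed. With n subjects, P(at least 2 DLTs) = 1 − (1 − d)^n − n·d·(1 − d)^(n−1). At d = 0.20:

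- n = 5: 1 − 0.32768 − 0.40960 = 0.26272
- n = 6: 1 − 0.26214 − 0.39322 = 0.34464

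| DLT rate | 5 subjects (Protocol) | 6 subjects (SAP) | Gap, points |
|---|---|---|---|
| 10% | 8.1% | 11.4% | 3.3 |
| 20% | 26.3% | 34.5% | 8.2 |
| one third | 53.9% | 64.9% | 11.0 |

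**4. Where the gate gap comes from.** It is exactly the chance of one DLT in the first five subjects followed by a DLT in the sixth, which is P(1 of 5) × d: 0.32805 × 0.10 = 0.033, 0.40960 × 0.20 = 0.082, 0.32922 × 0.33333 = 0.110. In that sequence SAP 2.2 reverts the dose or stops the study. Under the Protocol the Stage 2a gate has been passed with one DLT, and the three-DLT stop is not yet met on any count. However, 2/6 is exactly one third, so the dose already fails the tolerability test, which requires fewer than a third.

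**5. A reverse case.** The Protocol does not say whether the three-DLT stop counts only Stage 2b DLTs. Suppose it does, and apply the same stop to the 6-subject version. Take no DLT in subjects 1–5, a DLT in subject 6, and exactly two among subjects 7–11. Under the Protocol, subject 6 belongs to Stage 2b, so the count is three and dosing stops. With a 6-subject gate, subject 6 belongs to Stage 2a; the counts are one and two, and dosing continues. Probability: (1 − d)^5 × d × 10·d²·(1 − d)³.

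- 10%: 0.59049 × 0.10 × 0.07290 = 0.4%
- 20%: 0.32768 × 0.20 × 0.20480 = 1.3%
- one third: 0.13169 × 0.33333 × 0.32922 = 1.4%

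With cumulative counting both versions reach three DLTs, and this case disappears.

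**6. Illustration over 11 dosed subjects.** For gate size g, P(changed dose lost) = P(at least 2 of g) + sum over x = 0, 1 of P(x of g) × P(at least k of 11 − g). Here k = 3 − x for cumulative counting and k = 3 for Stage 2b only.

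| DLT rate | Cumulative, 5 vs 6 | Stage 2b only, 5 vs 6 |
|---|---|---|
| 10% | 12.8% vs 14.8% | 9.6% vs 12.2% |
| 20% | 43.6% vs 46.3% | 33.6% vs 38.3% |
| one third | 79.5% vs 80.9% | 68.6% vs 72.3% |

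The gaps are 1.4 to 2.7 points (cumulative) and 2.6 to 4.7 points (Stage 2b only), smaller than at the gate because the later stop catches part of the difference.

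**The case against.** The strongest reply is that this is editorial. Stage 2a runs only after a dose change. SAP 2.2 points the reader to the Protocol synopsis, and elsewhere the SAP already carries 5 and 11. In the main conflicting sequence both documents class the dose as not tolerable, and Protocol 8.3 lets the Medical Monitor and the investigators reduce the dose regimen at any time. On this view the 16 against 11 matters more than the Stage 2a number.

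Much of that stands, and it limits the size of the point. It does not remove the conflict. The tolerability definition and the discretion in Protocol 8.3 are not the count rule that sends the dose back or stops the study; the count rule is what differs. Both texts are current, no redaction explains the difference, and SAP 7 declares no departure. The 16 against 11 is a reason to correct the whole block rather than to leave the gate as it is.

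A reader might also infer that the fix has to be extended because changing Stage 2a alone would leave 5 + 10 = 15 against 16. The documents do not support that sum: the 10 never join Stage 2a subjects at the same dose. The reason to align the block is its disagreement with Protocol 6.1 and with the SAP's own 5 and 11.

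**Conclusion.** The inconsistency is real and should be fixed. SAP 2.2 misstates the Stage 2a denominator, and the gate as written triggers about 3 to 11 percentage points more often than the Protocol's. That figure is conditional on reaching Stage 2a and rests on assumed DLT rates from 10% to one third with independent subjects.

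Three stronger readings are tempting and not supported:

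- **That the 6-subject gate is always the more cautious one, or that it adds toxicity.** It usually stops more often, but the reverse case shows that this is not always so if only Stage 2b DLTs count.
- **That a whole-trial effect can be stated.** Any end-to-end figure applies the Protocol's Stage 2b stop to an SAP block that states none. Bringing in the chance of reaching Stage 2a also means assuming one DLT rate at 2, 3 and 5 applications. Such figures are illustrative only.
- **That the efficacy test is compromised.** The stated alpha and power and the 7-of-11 rule do not depend on the size of Stage 2a.

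The documents do not show where the 6 and 16 came from.

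**What to change.** In SAP 2.2, change Stage 2a from 6 to 5 subjects. In the same edit, align the block with Protocol 6.1 and with the SAP's own 5 and 11:

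- Opening sentence: a first stage of 5 evaluable subjects in place of 6 patients.
- Stage 1 rule 2: 5 in place of 6 evaluable subjects, in all four places.
- Stage 2: 11 in place of 16 total evaluable subjects at the final dose.
- Escalated-dose branch: the remaining patients, as in the Protocol, in place of up to 10 additional evaluable subjects.
- Delete the same-dose branch of Stage 2a. It cannot be reached, because Stage 2a is run only after escalation or de-escalation.

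If 6 is truly intended, declare it in SAP 7 and amend Protocol 6.1, its figure legend and the cap sentences in the Protocol synopsis, Protocol 10.2 and SAP 5.1.

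The main option costs nine small text edits (1 + 1 + 4 + 1 + 1 + 1), all in SAP 2.2, with no added patients or procedures.
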